- For Estimands #11, 12, 28, and 29, the ICE was changed. Time to fever clearance and time to parasite clearance will be censored at the time of intake of rescue/fever/prohibited medications that are taken within 3 days after treatment initiation.
- For Estimands #11 and 28 (analysis of fever clearance), only participants who had a temperature $>37.5^{\circ}\text{C}$ at the pre-dose visit or during the 24 hours following dosing will be included. If the fever medication was taken prior to dosing, participants will still be included for analysis. Strategies for intercurrent events will not apply.

- Analysis of Estimands #8, 9, 25, and 26, crude and PCR-adjusted efficacy 8 days after treatment, will not be conducted as no new information would be added.
- CCI
[REDACTED]
[REDACTED]
[REDACTED]
- Analysis of Estimands #13, 14, 15, 30, 31, and 32, time to recrudescence, re-infection, and re-emergence, will not be conducted as no new information would be added.
- For any analysis using axillary temperature, the temperature measured at other locations will be used instead without adjustment if the axillary temperature is not collected. The number of participants or visits with temperature measured at different body locations will be described in the footnote of the output.

8 Analysis Sets

8.1 Definition of Analysis Sets

The following Analysis Sets will be used:

Full Analysis Set (FAS)

The FAS will include all enrolled participants. Participants will be analyzed according to the treatment assigned at enrollment as per the Intention-to-Treat principle.

Safety Analysis Set (SAF)

All participants, who were administered any dose of any study intervention. Analyses will consider participants as treated.

PK Analysis Set (PKAS)

All participants, who receive ≥ 1 dose of study intervention, have no clinically important protocol deviations or important events affecting PK, and provide ≥ 1 measurable post-dose concentration. Participants will be analyzed per the actual study intervention they received. All PK analyses will be based on this analysis set for the final analysis.

Note that important protocol deviations or important events that lead to exclusion of participants from the PK Analysis Set are identified during the data review process.

The following table summarizes the use of the analysis sets in the different analyses.

Analyses	Analysis Set		
	FAS	SAF	PK Analysis Set
Baseline Characteristics	✓	✓*	
Previous and Concomitant Therapies	✓	✓*	
Efficacy: Primary Endpoint/Estimand	✓		
Efficacy: Secondary Endpoint/Estimand	✓		
Efficacy: CCI Endpoints/Estimands	✓		
Safety and Tolerability		✓	
PK analyses			✓

*only to be created if discordance between FAS and SAF is more than 5%

In addition to the above defined sets used for analysis, the Screened Analysis Set will be used only for the disposition table. The Screened Analysis Set contains all subjects who signed the informed consent.

9 General Specifications for Data Analyses

9.1 Treatment Cohorts

For Part A and Part B Cohort B0, participants are not randomized but different doses of M5717 and Pyronaridine are used. Unless otherwise indicated, all analyses will be presented separately for Part A and Part B Cohort B0. The two dose levels in Cohort B0 will be combined in the reports.

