control in order to provide reference safety data leveraging that the pyronaridine moiety is part of all the Part B cohorts. At the same time, the internal control arm will provide a benchmark for the efficacy to put the efficacy endpoints achieved in Cohort B1 and B2 into perspective. The pyronaridine dose will be adjusted according to the participants' weight following the dosing recommendations (based on the Pyramax SmPC dosing recommendations), with 720 mg being the maximum daily dose for participants weighing  $\geq 65$  kg. Pyramax is used as an internal control for efficacy and monitoring of resistance against pyronaridine. As it is a well-established product, clinical procedures will be limited and there will be no blood sampling for PK.

The primary objective of Part B is to determine the efficacy of the M5717-pyronaridine combination in adult and adolescent participants. The endpoint selected for the assessment of the efficacy is PCR-adjusted ACPR defined as absence of parasitemia (thick smear/microscopy), irrespective of axillary temperature, in participants who did not previously meet any of the criteria of ETF, LCF, or LPF at Day 29 after adjustment for parasitemia due to new infections as determined by genotyping using PCR techniques. PCR-adjusted ACPR is the regulatory accepted endpoint for the assessment of antimalarials efficacy according to WHO and EMA and has been the basis for granting authorization for several ACT combinations recently (Eurartesim EMA/739355/2011). Additional endpoints such as fever clearance time and clinical signs and symptoms of malaria have been included, being endpoints traditionally evaluated in malaria clinical studies.

The population selection rationale in Part B that involves an extension to adolescents  $\geq 12$  years of age is based on:

- Demonstration of good tolerability in Part A in the adult population that permits a full dose in Part B.
- Good tolerability in 16 adult and adolescent participants with a body weight  $\geq 45$  kg in Cohort B0 with the higher dose before including adolescents on 500 mg dose of M5717 (body weight  $< 45$  kg).
- Evaluation of whether the predicted exposure is reached in the first 9 adolescent participants treated with 500 mg dose of M5717 before including further adolescent participants at that dose.

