Based on population PK modeling and simulation, assuming allometric scaling, doses were adjusted for participants  $\geq 24$  to  $< 45$  kg for 1 day (see [Figure 1](#)) and 2 days (see [Figure 2](#)). A dose of 500 mg M5717 in participants with a body weight of  $\geq 24$  to  $< 45$  kg (left pink box plots) is expected to lead to exposure similar to that after administration of 660 mg in adults (right blue box plot). The 1-day and 2-day exposures (90% prediction interval) in the adult and adolescent population are within the 1,440 mg exposure (grey area).

In addition, preliminary PK/PD modeling and simulation suggested that the median ACPR28 efficacy is predicted to between 69.7% to 98% for Cohorts B0 and B1 and 78.9% to 99.3% for Cohort B2 (data on file).

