#### **9.4.4                   Sequence of Analyses**

Two interim analyses will be performed by the IDMC. The IDMC will evaluate the interim efficacy and safety results after completion of Part A (first interim analysis) and after 25 participants have been enrolled and treated in Cohort B0 of Part B (second interim analysis). Cohort B0 will include 16 participants (approximately 8 adults and 8 adolescents) with a body weight  $\geq 45$  kg. Should these participants not meet the safety stopping criteria, another 9 adolescent participants with a body weight  $< 45$  kg (with adapted dose) for M5717 (500 mg) will be included. Lack of efficacy will be monitored in the first 16 participants recruited in Cohort B0. Lack of efficacy is defined as the requirement to administer rescue medication to  $\geq 5$  of the first 16 participants randomized and treated in Cohort B0 (if predicted exposure is observed) until Day 29.

The scope of the analyses by IDMC will be evaluation of safety, efficacy, and PK, and assessment for potential dose adaptations.

## 10

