9.2 Investigational Medical Product (IMP)

The IMP is the combination of M5717 and pyronaridine. For Part A, participants are administered 330 mg of M5717 and 260 mg of pyronaridine. For Part B Cohort B0, participants are administered different dose levels according to body weight: 500 mg of M5717 and 360 mg of pyronaridine for participants ≥ 24 to < 45 kg, 660 mg of M5717 and 540 mg of pyronaridine for participants ≥ 45 to < 65 kg, and 660 mg of M5717 and 720 mg of Pyronaridine for participants ≥ 65 kg.

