16.1.4.1 Listings and Tables

- Individual concentrations and descriptive statistics of concentrations by analyte, and group
- Individual PK parameters and descriptive statistics of PK parameters by analyte, and group
- Individual dose normalized PK parameters and descriptive statistics of dose normalized PK parameters by analyte, and group
- Individual diagnostic PK parameters by analyte, matrix, day and group

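### The SAP plans no PK summary by M5717 dose within Cohort B0, although the protocol asks whether 500 mg in participants under 45 kg reaches the predicted exposure

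*SAP*

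**What the plan says.** **Reporting rule.** SAP 9.1 presents Part A and Cohort B0 separately and adds: "The two dose levels in Cohort B0 will be combined in the reports". SAP 9.3 presents tables and figures by Part unless otherwise specified. SAP 9.2 confirms that within Cohort B0 "participants are administered different dose levels according to body weight": 500 mg M5717 with 360 mg pyronaridine, 660 mg with 540 mg, or 660 mg with 720 mg. The two levels being combined are thus the M5717 levels, and three pyronaridine doses are combined with them.

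**PK outputs.** SAP 16.1.4.1 lists "Individual PK parameters and descriptive statistics of PK parameters by analyte, and group", with matching entries for concentrations and dose-normalised parameters. In SAP 16.1.4.2 the mean concentration plots are by analyte and the boxplots carry no grouping. The only place the SAP spells out a dose group is the Cox model in SAP 14.5, where it is Part A versus Cohort B0.

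**The protocol's question.** Among the reasons for extending Part B to adolescents, protocol 4.2 gives: "Evaluation of whether the predicted exposure is reached in the first 9 adolescent participants treated with 500 mg dose of M5717". Protocol 4.3 states the prediction: 500 mg in the lower weight band "is expected to lead to exposure similar to that after administration of 660 mg in adults". Protocol 6.5 wants under- and overexposure avoided in both weight bands. SAP 7 records that Cohorts B1, B2 and B3 were not enrolled.

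**The concern.** The 500 mg dose rests on population PK simulation with allometric scaling. The planned low-weight adolescents are where that prediction meets data, and protocol 4.2 regards PK in older children as groundwork for later studies in younger ones. A summary that mixes them with the 660 mg participants estimates neither group. An under- or overexposed lower band would be blended into a Cohort B0 figure dominated by the heavier participants, and the geometric mean, its 95% CI and the geometric CV that the SAP specifies for PK parameters would never be produced for the group in question.

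**Working it through.** **Inputs.** Protocol 9.4.4 gives the planned make-up: "Cohort B0 will include 16 participants (approximately 8 adults and 8 adolescents) with a body weight" of at least 45 kg (660 mg M5717), then "another 9 adolescent participants with a body weight" below 45 kg (500 mg). The interim review follows "after 25 participants have been enrolled and treated in Cohort B0 of Part B (second interim analysis").

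**Plan's own figure.** 16 + 9 = 25, which reproduces the stated cohort size. The 500 mg share is 9/25 = 36%.

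**Dilution of the geometric mean.** Let R be the exposure ratio of 500 mg to 660 mg participants. The prediction of similar exposure is R near 1. The pooled geometric mean, relative to the 660 mg value, is R^(9/25).

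| True R | Pooled relative to 660 mg |
|---|---|
| 0.50 | 0.78 |
| 0.70 | 0.88 |
| 0.75 | 0.90 |
| 1.50 | 1.16 |
| 2.00 | 1.28 |

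A 30% shortfall shows as 12%, and a halving as 22%.

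**Does the pooled spread reveal it?** The documents give no PK variability, so I assume a within-group CV of 30%, 50% or 80%. The log-scale variance within groups is ln(1 + CV²); pooling adds 0.36 × 0.64 × (ln R)². For R = 0.70 the addition is 0.2304 × 0.1272 = 0.029.
- CV 30%: 0.0862 + 0.0293 = 0.1155, a pooled geometric CV of about 35%.
- CV 50%: 0.2231 + 0.0293 = 0.2524, about 54%.
- CV 80%: 0.4947 + 0.0293 = 0.5240, about 83%.

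A rise of three to five percentage points would not signal a problem.

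**Does dose normalisation help?** Not for this question. If both doses give similar exposure, as predicted, the M5717 values per mg differ by 660/500 = 1.32 by design. If instead exposure is proportional to dose, so that the 500 mg group sits at 500/660 = 0.76 of the 660 mg value, the dose-normalised values agree. Pooled dose-normalised figures look most uniform when the prediction fails in that way.

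**What a split would deliver.** With s = √ln(1 + CV²), the 95% CI factor for one geometric mean is exp(t × s/√n), with t on n − 1 degrees of freedom. For the ratio it is exp(t × s × √(1/9 + 1/16)), with t on 23.

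| Assumed CV | 500 mg geometric mean, n = 9 | Ratio 500:660, 9 vs 16 |
|---|---|---|
| 30% | ×/÷ 1.25 | ×/÷ 1.29 |
| 50% | ×/÷ 1.44 | ×/÷ 1.50 |
| 80% | ×/÷ 1.72 | ×/÷ 1.83 |

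For an observed ratio of 0.70, the interval is 0.54 to 0.90 at a CV of 30% and 0.47 to 1.05 at 50%.

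**The case against.** **The data are not lost.** A reader might infer that pooling leaves the trial unable to show whether 500 mg reaches the predicted exposure. The documents do not support that. SAP 9.3 sorts listings by M5717 dose, SAP 16.1.4.1 lists individual concentrations and parameters, and SAP 16.1.4.2 plans individual profiles. Nine values can be read off. This stands, but it leaves the reader to compute the summary statistics.

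**The question belonged to the IDMC.** The sentence in protocol 4.2 goes on to make the check a condition for enrolling more adolescents at that dose. Protocol 6.5 gives dose adjustment to the IDMC with internal PK/PD support, and SAP 6 covers end-of-study analyses, so SAP 9.1 need not bind that review. The gate lapsed when the later cohorts were not opened. This also stands in part. But neither document specifies a weight-band summary for the IDMC, and an interim review does not replace reporting of the PK objective, which covers adults and adolescents in Cohort B0.

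**Group may mean dose.** It may: SAP 15.4 groups laboratory plots by M5717 dose. That reading would put SAP 16.1.4 at odds with SAP 9.1, so a definition is needed either way.

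**Other splits.** A reader might also infer that safety at 500 mg is visible only in listings. The laboratory plots in SAP 15.4 contradict that. Pooling ACPR follows the primary estimand, which treats the weight-banded regimen as one treatment. For pyronaridine, dose-normalised statistics answer part of the two-fold dose range, but not whether exposure is alike across weight bands.

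**Small n.** The split is imprecise, as the intervals show. The PK objective is descriptive, so this limits the claim rather than the usefulness of the table.

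**Conclusion.** The point holds as a reporting gap in PK. Read with SAP 9.1, 9.3 and 14.5, SAP 16.1.4 plans no end-of-study PK summary by M5717 dose, while the protocol poses an exposure question specific to 500 mg. The pooled geometric mean would show about 12% for a 30% shortfall, and neither the pooled CV nor dose normalisation would bring it to light. It is not a defect in data collection or in the primary efficacy analysis.

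This rests on the planned 16 and 9 participants all entering the PK Analysis Set. The 30% shortfall and the CVs of 30% to 80% are assumptions for illustration; the predicted exposures are in figures missing from the available text, so no comparison with them was possible.

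**What to change.** - In SAP 9.1, exempt PK from the rule that combines the Cohort B0 dose levels.
- In SAP 16.1.4, define *group* as Part A and, within Cohort B0, M5717 dose.
- Present PK concentration and parameter summaries, mean plots and boxplots for 660 mg and 500 mg separately (planned n = 16 and 9) beside the combined Cohort B0 column, and set the 500 mg results against the exposure predicted in protocol 4.3.
- Summarise pyronaridine PK by its three dose bands (360, 540 and 720 mg).
- Optionally, show ACPR and related TEAEs by M5717 dose as description only, leaving the primary estimand unchanged.

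This is a cheap improvement: no new data, a few extra columns and figures. The downside is wide intervals at n = 9, so the text should say that the split describes and does not test.

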9.2 Investigational Medical Product (IMP)

The IMP is the combination of M5717 and pyronaridine. For Part A, participants are administered 330 mg of M5717 and 260 mg of pyronaridine. For Part B Cohort B0, participants are administered different dose levels according to body weight: 500 mg of M5717 and 360 mg of pyronaridine for participants ≥ 24 to < 45 kg, 660 mg of M5717 and 540 mg of pyronaridine for participants ≥ 45 to < 65 kg, and 660 mg of M5717 and 720 mg of Pyronaridine for participants ≥ 65 kg.

9.3 Presentation of Tables/Listings/Figures

Tables and Figures will be presented by Part, unless otherwise specified. A “Total” column will be included in non-efficacy tables. In the individual participant data listing all individual data will be listed as measured. Unless otherwise specified, all listings will be sorted by Part, M5717 dose, subject ID, and scheduled time point.

Repeated and unscheduled measurements included in the listings will not be used for statistical analyses or summaries, unless the repeated measurement was performed due to unreliable values/technical reasons, e.g., clotted samples. They will be flagged as such in the listings.

Presentation of continuous and qualitative variables

Unless otherwise specified, continuous variables will be summarized using descriptive statistics, i.e., the number of participants with non-missing values (n), the number of participants with missing values (nmiss), mean, standard deviation, median, 25th percentile (Q1) and 75th percentile (Q3), minimum, and maximum.

Qualitative variables will be summarized by frequency counts and percentages. Unless otherwise stated the calculation of proportions will be based on the number of participants of the analysis set of interest. Therefore, counts of missing observations will be included in the denominator and presented as a separate category.

Descriptive statistics by nominal visit or time point, e.g., for laboratory measurements, will include only data from scheduled visits.

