9.4 Analysis visit windows

Each participant will be followed up till Day 43 (\pm 2 days) or the day of premature discontinuation, including 4 continuous days (72 hours post first dose) in the hospital after admission, followed by 5 out-patient visits on Days 8, 15, 22, 29, and 43 (or day of premature discontinuation).

The time window is \pm 30 minutes for each scheduled timepoint on Day 1 through Day 4. The visit window is \pm 1 day for Day 8 and \pm 2 days for Days 15, 22, 29 and 43.

In case any assessment occurs outside of the defined timepoint/visit window, it will be allocated to “unscheduled”. These visits will not be included in descriptive statistics by nominal visit or time point and will be flagged in subject data listings. In case too many measurements are observed outside of the defined visit windows, it will be decided on an individual basis whether those can be allocated to scheduled visits in a reasonable manner during data review before database lock.

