14.1 Crude and PCR-adjusted ACPR at Various Timepoints

Crude ACPR 28 and 42 days after first dose is defined as absence of parasitemia (parasite count = 0) from thick smear/microscopy, irrespective of axillary temperature, in participants who did not previously meet any of the criteria of ETF, LCF, or LPF.

PCR-adjusted ACPR 28 and 42 days after first dose is defined as absence of parasitemia (parasite count = 0) from thick smear/microscopy after adjustment for parasitemia due to new infections as determined by genotyping using PCR techniques, irrespective of axillary temperature, in participants who did not previously meet any of the criteria of ETF, LCF, or LPF. By PCR-adjustment all participants with parasitemia due to a new infection are considered responders. Note that PCR-adjusted ACPR 28 days after first dose is the endpoint of the primary estimand for Part B Cohort B0.

In order to derive the population-level summary of the estimands, different intercurrent events (ICEs) will be considered. ICE as defined by the study protocol will be identified and handled as described in the following if the ICE takes place before 28 or 42 days post treatment:

- **Intake of rescue medication:** Filtering concomitant medications programmatically for all artemisinin-based combination therapies (artemether-lumefantrine, artesunate-amodiaquine, dihydroartemisinin-piperaquine, artesunate-sulphadoxine-pyremethamine), chloroquine, quinine, halofantrine, primaquine and by medical review. A composite variable strategy is applied, i.e., the primary endpoint is considered as failure (= presence of parasitemia and no ACPR).
- **Intake of prohibited medication that impacts treatment effect (e.g., drug with antimalarial activity) at any timepoint:** A treatment policy strategy is applied, i.e., treatment effect is estimated regardless of the ICE.
- **Experience of any event that affects absorption (i.e., vomiting within the study intervention absorptive period of $2 \times \text{median tmax}$) or immune response (severe immunocompromised participants):** Filter AE data programmatically for preferred term (PT) “Vomiting” within the System Organ Class (SOC) “Gastrointestinal disorders” and by medical review. A treatment policy strategy is applied, i.e., treatment effect is estimated regardless of ICE.

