- **Premature study discontinuation due to lack of efficacy:** Participants who have primary reason for early termination set as “Lack of efficacy” on Study Termination eCRF. A composite variable strategy is applied, i.e., endpoint is considered as failure.
- **Death due to malaria:** Filter SAEs programmatically for fatal events with outcome “death” and by medical/safety review. Death cases for which the primary reason is ticked as “progressive disease and/or disease-related condition” qualify as death due to malaria. A composite variable strategy is applied, i.e., endpoint is considered as failure.

Participants who did not previously meet any criteria of ETF, LCF, or LPF, have no ICE, and are missing parasitemia data at the specified timepoint after first dose will be included in the denominator of the proportion and will be counted as ‘N/A’ in the summary table.

The population-level summaries are the proportion of participants achieving PCR-adjusted/Crude ACPR 28/48 days after first treatment (ACPR rates). ACPR rates will be estimated with 95% confidence intervals. Confidence intervals will be derived by use of Wilson’s score method.

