14.2 Early Treatment Failure (ETF)

ETF is defined as meeting any of the following:

- a) Danger signs or severe malaria 1, 2, or 3 days after treatment (i.e., between Days 2 and 4), in the presence of parasitemia (parasite count > 0).
- b) Parasitemia 2 days after treatment higher than on day of treatment (defined as count at baseline), irrespective of axillary temperature.
- c) Parasitemia 3 days after treatment with temperature $\geq 37.5^{\circ}\text{C}$.
- d) Parasitemia 3 days after treatment $\geq 25\%$ of parasite count on day of treatment (defined as the count at baseline).

The same ICEs and strategies as defined for ACPR (see Section 14.1) will be applied for ETF, however, limited to events that occur before or at Day 4 (i.e., 3 days after treatment). Failure is considered presence of ETF.

The population-level summary is proportion of participants with ETF (ETF rate). ETF rate will be estimated with 95% confidence intervals. Confidence intervals will be derived by use of Wilson's score method.

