14.3 Late Clinical Failure (LCF)

LCF is defined as meeting any of the following:

- a) Danger signs or severe malaria in the presence of parasitemia on any day between 4 and 28 days after treatment (i.e., between Days 5 and 29) in participants who did not previously meet any of the criteria of ETF.
- b) Presence of parasitemia on any day between 4 and 28 days after treatment with temperature $\geq 37.5^{\circ}\text{C}$ in participants who did not previously meet any of the criteria of ETF.

The same ICEs and strategies as defined for ACPR (see Section 14.1) will be applied for LCF, however, limited to events that occur between 4 and 28 days after treatment (i.e., between Days 5 and 29). Failure is considered presence of LCF.

The same analyses and population-level summaries as described for ETF will be applied for LCF.

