16.1.2 General Specifications for PK Concentration and PK Parameter Data

PK concentration samples taken before the first drug administration (predose samples) will be assigned a time of 0 hours, as if the sample had been taken simultaneously with the study intervention administration.

In case pre-dose samples have been taken after the subsequent dosing, the resulting concentrations will be included in concentration listings but excluded from descriptive statistics of concentrations and from PK parameter estimation. For post-dose samples collected outside the allowed time window, the resulting concentrations will be included in descriptive statistics of concentrations and in PK parameter estimation.

Values below the lower limit of quantification (BLQ) will be taken as zero for summary statistics of PK concentration data, PK parameter estimation (e.g., AUC) and for graphical presentations.

In case profiles have a measurable pre-dose concentration less than or equal to 5% of its C_{max} value, the participant's data will be included in the PK and statistical analyses without any adjustments. If the pre-dose value is greater than 5% of the C_{max} , the participant's data for this period will be included in the PK evaluation but excluded from descriptive and further statistical evaluation after agreement with the sponsor.

Missing concentrations (e.g., no sample, insufficient sample volume for analysis, no result or result not valid) will be reported and used generally as "N.R.". A participant who withdraws prior to the last planned observation will be included in the analyses up to the time of discontinuation.

PK concentrations which are erroneous due to a sampling processing or analytical error (as documented in the bioanalytical report) may be excluded from the PK analysis if agreed by the Sponsor.

PK concentrations and PK parameters excluded from summary statistics will not be included in mean figures.

If less than 3 post-dose concentrations are available within a PK profile, derived PK parameters will be flagged and might be excluded from statistical evaluation after consultation with the Sponsor.

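### Read literally, SAP 9.3 and 9.4 drop unscheduled and late films from the failure endpoints; separately, SAP 14.6 cuts parasite clearance time to calendar days

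*SAP*

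**What the plan says.** **General rules.** SAP 9.3: "Repeated and unscheduled measurements included in the listings will not be used for statistical analyses or summaries". The only exception is a repeat made because a value was unreliable or for a technical reason. A separate sentence in 9.3 restricts by-visit descriptive statistics to scheduled visits. SAP 9.4 sets windows of ±30 minutes for Days 1 to 4, ±1 day for Day 8 and ±2 days for Days 15, 22, 29 and 43. It continues "In case any assessment occurs outside of the defined timepoint/visit window, it will be allocated to" the unscheduled category. It also allows re-allocation at data review: "In case too many measurements are observed outside of the defined visit windows, it will be decided on an individual basis". No threshold is given.

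**Efficacy rules.** SAP 14.3 defines LCF by "Presence of parasitemia on any day between 4 and 28 days after treatment with temperature" at or above the fever cut-off. SAP 14.4 defines LPF in the same way for 7 to 28 days, below the cut-off. ETF criterion c in 14.2 is "Parasitemia 3 days after treatment with temperature" at or above the cut-off, and criterion d compares the 3-day count with baseline. ACPR in 14.1 requires none of these failures. Participants with no failure and no intercurrent event who "are missing parasitemia data at the specified timepoint after first dose will be included in the denominator of the proportion" are shown as N/A. Protocol 8.1 has films read every 6 hours to 72 hours, at the out-patient visits, and at any unscheduled visit.

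**PK contrast.** SAP 16.1.2 has its own rule: "For post-dose samples collected outside the allowed time window, the resulting concentrations will be included in descriptive statistics of concentrations". Section 14 has no such sentence for films.

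**Parasite clearance.** SAP 14.6 measures it in days and censors by day. SAP 9.9 calculates times as a date difference plus 1, and uses datetimes only for times in hours. SAP 14.5 measures fever clearance in hours.

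**The concern.** Two programmers can each follow the SAP and obtain different results. One applies the section 14 definitions to every film. The other applies 9.3 and drops films from unscheduled visits or outside a window. The failure endpoints feed ACPR, and PCR-adjusted ACPR at Day 29 is the primary endpoint for Cohort B0. In a cohort of 25, one participant is 4 percentage points.

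The ±30 minute window also covers the 72 h film, which is the only Day 4 film in protocol Table 2 and the basis of ETF criteria c and d. If taken 31 minutes late, it is unscheduled by default.

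A negative Day 29 film taken outside Days 27–31 is N/A by default. Whether it is re-allocated depends on an undefined trigger, judged at data review in an open-label, non-randomised cohort.

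For parasite clearance, the day unit discards most of the information in the 6-hourly films and makes the result depend on the clock time of dosing.

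**Working it through.** **1. The plan's own precision figure.** Protocol synopsis: n = 50, expected rate 95%, lower Wilson 95% bound about 85%. The Wilson limits are [p + z²/2n ± z√(p(1−p)/n + z²/4n²)] / (1 + z²/n), with z = 1.96. For p = 0.95 and n = 50, the lower limit is (0.9884 − 0.0716)/1.0768 = 85.1%. Averaged over the binomial distribution it is 85.3%. The figure is reproduced and is not in dispute.

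**2. Days with no scheduled film.** The windows cover Days 7–9, 13–17, 20–24 and 27–31.
- LCF range, Days 5–29 (25 days): Days 5, 6, 10, 11, 12, 18, 19, 25 and 26 lie outside every window, so 9 of 25.
- LPF range, Days 8–29 (22 days): Days 10, 11, 12, 18, 19, 25 and 26 lie outside, so 7 of 22.

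Under the literal rule, a positive film on those days is not used.

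**3. When a positive film would actually be lost.** All of the following must hold:
- no recorded rescue (SAP 14.1 counts rescue as failure whatever the visit type);
- no discontinuation for lack of efficacy;
- no malaria death;
- no later positive scheduled film.

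For PCR-adjusted ACPR the parasitemia must also not be a new infection, since "By PCR-adjustment all participants with parasitemia due to a new infection are considered responders". The same conditions apply to a late 72 h film meeting criterion c or d: protocol 6.8.1 and 7.1 make that finding a reason for rescue, and rescue by Day 4 counts as ETF.

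**4. Size of one missed failure** (the count is assumed; the cohort sizes are those planned).

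| Cohort | With the failure | Without it |
|---|---|---|
| B0, n = 25 | 24/25 = 96.0% (80.5–99.3%) | 25/25 = 100% (86.7–100%) |
| Part A, n = 12 | 11/12 = 91.7% (64.6–98.5%) | 12/12 = 100% (75.8–100%) |

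**5. Parasite clearance in days.** With dosing at clock hour h and clearance at t hours, date difference plus 1 equals floor((h + t)/24) + 1. For the 12 post-dose films (6 to 72 h):

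| Dosed at | 1 day | 2 days | 3 days | 4 days |
|---|---|---|---|---|
| 08:00 | 6–12 h | 18–36 h | 42–60 h | 66–72 h |
| 16:00 | 6 h | 12–30 h | 36–54 h | 60–72 h |
| 20:00 | none | 6–24 h | 30–48 h | 54–72 h |

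Twelve film times become four values. A 36 h clearance gives floor(44/24) + 1 = 2 days if dosed at 08:00, and floor(52/24) + 1 = 3 days if dosed at 16:00. Over all whole-hour dosing times, 9 of the 12 film times can take two values; only 24, 48 and 72 h are fixed.

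**6. A side result that matters for the fix.** Calendar Day 4 contains the 66 and 72 h films if dosed at 08:00, 60–72 h at 16:00 and 54–72 h at 20:00. A rule that uses all films by date would therefore not identify one film as the 3-day film for ETF.

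**The case against.** The conflict rests on a literal reading of one sentence in a section about presentation. SAP 9.4 states a narrower consequence for out-of-window data, namely exclusion from by-visit descriptive statistics. Section 14 gives endpoint-specific definitions, and a specific rule ordinarily overrides a general one. The PK sentence in 16.1.2 can be read as an example of exactly that. This is a fair reading and may be what the authors intended. It does not close the point: 9.3 already has its own by-visit sentence, so the broader one, which names statistical analyses, appears to mean something more, and the SAP gives no order of precedence.

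Positive films are also largely protected by the routes in step 3 of the working. That stands and limits the size. The protection is not complete: among the rescue circumstances that protocol 6.8.1 lists, none names parasitemia found after Day 8, although Table 1 allows rescue as required and 6.6 provides it if the intervention fails to cure.

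On parasite clearance, the protocol fixes no unit, the endpoint is secondary, and no arms are compared after early termination. All of this stands. How many participants would be tied cannot be taken from the documents. On assumed inputs (median 18–48 h, log-SD 0.2–0.5, dosing uniform from 08:00 to 20:00), 23% to 93% of pairs with different film times become ties and at most 1.8% reverse order. That range is too wide to size the loss.

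**Conclusion.** The point holds in two parts.

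(a) The SAP is ambiguous on whether unscheduled and out-of-window films count towards ETF, LCF, LPF and ACPR. A reader might infer that failures will be lost and the B0 rate inflated. The documents do not support that: they show no affected film, section 14 may prevail, and several routes still record the failure. If one were lost, the B0 estimate would move from 96% to 100% and its lower limit from 80.5% to 86.7%. A reader might also take the 4 points that each N/A costs as the gain from repair. It is not, because a fixed window rule still leaves a participant with a late negative film as N/A. What the repair removes is discretion.

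(b) The day unit for parasite clearance is the clearer defect. It coarsens the Kaplan-Meier median and the Cox model and makes the value depend on dosing hour. A reader might call it a departure from the protocol, but the protocol states no unit. It is lost resolution in a secondary endpoint. This part assumes that days are calculated by the date rule in 9.9, the only formula the SAP gives for times not in hours.

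Severity: minor to should-fix. Confidence: medium.

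**What to change.** 1. Limit the exclusion in SAP 9.3 and 9.4 to descriptive tables by nominal visit. State in section 14 that LCF, LPF and parasite clearance time use all post-dose films, scheduled or not, by actual date and time. For ETF criteria b to d, use the films collected for the nominal 48 h and 72 h timepoints even if outside ±30 minutes, and not other films from the same calendar day.

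2. Replace the re-allocation discretion in 9.4 with one rule, fixed before data review and applied alike to positive and negative films. Films on Days 27–31 give Day 29 status and films on Days 41–45 give Day 43 status; where a window holds several, a positive film decides. Films outside these windows leave the participant N/A. Add a sensitivity analysis that uses a later negative film, without intervening antimalarial treatment, for N/A participants.

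3. Compute parasite clearance time in hours with the datetime formula already in 9.9. Where 14.6 censors at the last microscopy assessment, use its date and time.

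The cost is SAP wording and programming only; no new data are needed. Using unscheduled films may show slightly more failures, and some participants with a late negative film remain N/A in the main analysis.
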